4.3 Masking

This trial will be single masked, with most members of the study team including the lead biostatistician masked to the comparator group (treatment condition) randomly assigned to each participant. Due to the nature of the intervention, masking interventionists or study participants to the comparator received is not feasible. The PI and research coordination team will conduct fidelity monitoring activities that may reveal the treatment assignment of individual participants.

5. Study Population

The study population for this research is adult and adolescent patients, and healthcare providers and staff from St. Luke's Health System in Idaho. Aim 1 will include up to approximately 2,400 patients and 2,400 providers and staff. Aim 2 will include a subset of 660 Aim 1 participants who report elevated levels of mental distress (330 patients, and 330 providers or staff). SLHS employs over 14,000 people

MHAPPS Trial Protocol

SLHS Applied Research

December 30,2020

and serves nearly half of the population of Idaho; a recent CDC report indicated that over 40% of adults reported elevated levels of mental distress during the COVID-19 pandemic. The source population is adequately large to meet this study's recruitment goals.

5.1 Inclusion & Exclusion Criteria

Inclusion criteria are intentionally broad, to facilitate recruitment of a study sample that is maximally representative of the population of SLHS patients, providers, and staff.

5.1.1 Inclusion & Exclusion Criteria: Aim 1

Provider & Employee Inclusion Criteria

- Provider or Employee at St. Luke's Health System
- Adults ≥ 18 years of age
- Proficient in spoken and written English language

Provider & Employee Exclusion Criteria

- Individuals who are unable or unwilling to provide informed consent to participate
- Individuals who are study staff for this study or the SPARC Trial

Patient Inclusion Criteria

- Patient at a SLHS primary care site
- Current MyChart account user
- Adults ≥ 18 years of age
- Minors 12-17 years of age
- Proficient in spoken and written English language

Patient Exclusion Criteria

- Individuals who are unable or unwilling to provide informed consent to participate.
- Individuals who are participants in the SPARC Trial
- Individuals who have not had a primary care visit in the past 12 months

5.1.2 Inclusion & Exclusion Criteria: Aim 2

Provider & Employee Inclusion Criteria

- Moderate or high score for loneliness, suicide ideation, psychological stress, anxiety, or depression:
 - NIH Toolkit Loneliness raw score of 13 or greater or
 - C-SSRS score of 3 or greater; or

MHAPPS Trial Protocol

SLHS Applied Research

December 30,2020

- NIH Toolkit Perceived Stress raw score of 31 or greater for adults; or
 - GAD7 score of 11 or greater; or
 - PHQ9 score of 10 or greater
- Access to a phone for the duration of the study with the ability to receive text messages and phone calls

Provider & Employee Exclusion Criteria

- Individuals who are unable or unwilling to provide informed consent to participate
- Individuals who are in acute crisis as determined by the person conducting the consent process
- Individuals who are study staff for this study or the SPARC Trial
- Individuals who are enrolled as participants in the SPARC comparative effectiveness clinical trial (SPARC Aim 1). Providers or employees who received training related to SPARC and/or who completed the SPARC provider satisfaction survey are not excluded from participating in MHAPPS

Patient Inclusion Criteria

- Moderate or high score for loneliness, suicide ideation, psychological stress, anxiety, or depression:
 - NIH Toolkit Loneliness raw score of 13 or greater for adults or 16 or greater for adolescents; or
 - C-SSRS score of 3 or greater; or
 - GAD7 score of 11 or greater; or
 - PHQ9 score of 10 or greater; or
 - NIH Toolkit Stress raw score of 31 or greater for adults or 33 or greater for adolescents
 - *Note: validated youth versions of the NIH Toolkit assessments (loneliness and perceived stress), and PHQ-A tools will be used for adolescents ; the C-SSRS and GAD7 tools are validated for use with both adults and adolescents.*
- Access to a phone for the duration of the study with the ability to receive text messages and phone calls

Patient Exclusion Criteria

- Patients who are unable or unwilling to provide informed consent/assent to participate (or whose legally authorized representative is unable to provide consent in the case of adolescents). Examples may include but are not limited to patients who present with cognitive impairment, as determined by the person conducting the consent process, that would preclude their ability to consent (i.e. acute psychosis, intoxication, or intellectual disability).
- Individuals who are in acute crisis as determined by the person conducting the consent process

MHAPPS Trial Protocol

SLHS Applied Research

December 30,2020

5.2 Recruitment Strategy

A random selection of MyChart users who have attended a primary care visit at SLHS within the past 12 months will be recruited for the Aim 1 survey through a message including a REDCap survey link sent to their MyChart account or email. A comprehensive list of providers and employees and their email addresses will be obtained from a contact in the SLHS Human Resources Department, Digital and Analytics, or another appropriate department and a random sample of providers and employees will be selected using appropriate software. Those randomly selected will be recruited for the Aim 1 survey through an email message including a REDCap survey link. The Aim 1 survey will include an option to opt out of being contacted by study staff for participation in a follow-up study if they are potentially eligible. Participants who indicate interest in the follow-up study who also report elevated mental distress will be the source population for Aim 2. Recruitment for Aim 2 will involve study staff contacting potential participants to describe the Aim 2 clinical trial, conduct informed consent, and enroll interested patients into the trial. Recruitment-related emails will be either automatically sent via REDCap, sent from the [contact] email address, sent from the PI, delegated study staff, or sent via MyChart. In the event that there are more eligible and interested potential participants than available space in the trial, potential participants will be invited to participate in the order in which they completed the Aim 1 Survey.

For Aim 1, informed consent and study enrollment will be completed by the participant electronically through REDCap, with study staff available by phone or email to answer any questions. For Aim 2, informed consent and study enrollment will be conducted by trained study staff, typically a Research Coordinator over the phone or via video chat. All staff conducting informed consent and study enrollment will be trained in human subjects' protection and study procedures and will be delegated to do so by the study PI.

5.3 Retention

A variety of methods will be used to improve retention of research participants in the clinical trial. A contact sheet will be provided at enrollment allowing patients to share additional contact information (including alternative phone numbers, email addresses, or social media contact information) that may be used to contact participants for retention purposes. A primary cell phone number and an email address are required; providing additional sources of contact on the contact sheet is optional for study participants. Email, text messages, phone calls, or other forms of contact may be used for retention purposes or to assist with scheduling and completing six-month follow-up surveys. Retention methods are further described in protocol section *10.2 Lost to Follow-Up*.

5.4 Populations for Analyses

Analyses will be completed using the following populations:

1. **Intention to Treat (ITT) Analytic Population:** Data for all participants that complete study enrollment will be included in this dataset.
2. **Safety Analysis Population:** The dataset shared with the Data & Safety Monitoring Board for safety analysis will include data for all participants who completed study enrollment (e.g., the ITT Analytic Population Dataset).
3. **Per-Protocol Analysis Population:** Data for a subset of participants who were retained for the full study, were sent all 11 caring text messages, and received a phone call if randomized to the CC+ intervention (as outlined in protocol section 9) will be included in this dataset.
4. **Additional populations:** Additional datasets may be developed to complete sensitivity analyses, for example, where missing data have been imputed using different techniques.

6. Study Procedures

Aim 1: Cross Sectional Survey (Email REDCap survey link for providers and staff; send REDCap survey link via MyChart or email for patients)

- Aim 1 study enrollment and informed consent
- Aim 1 Survey
 - Demographics questions
 - C-SSRS (suicide risk)
 - NIH Toolbox Social Relationship Scales (loneliness, stress)
 - INQ (defeat, entrapment, perceived burdensomeness, and thwarted belongingness)
 - PHQ-9 (depression)
 - GAD-7 (anxiety)
 - COVID-19 beliefs and practices survey (brief)

Aim 2: Baseline / Enrollment (Subset of Aim 1 participants; see below)

- Aim 2 study enrollment and informed consent (phone call with Research Coordinator or study staff to complete via REDCap)
- Aim 2 Baseline assessments (Email or text REDCap survey link)
 - Baseline survey (Socio-economic status, gender identity, sexuality, religion, and alcohol and illicit drug use)
 - Expanded COVID-19 beliefs and practices survey (additional questions related to impact of COVID-19 on the individual, and his/her/their family, friends, and community)
 - Contact Sheet to collect alternative forms of contact for study participant

Aim 2: Caring Contacts Interventions (see description of interventions in section 9)

- **CC+:** 1 call, within 2 weeks of enrollment, and 11 caring text messages, sent from Hotline

follow-up specialists according to a standardized schedule over a 6-month period

- **CC:** 11 personalized caring text messages sent from Hotline follow-up specialists according to a standardized schedule over a 6-month period

6 Month Outcome Assessment (\pm 4 weeks variance window) (REDCap survey link sent via email or text)

- Aim 2 6-Month Outcome Assessments:
 - C-SSRS (suicide risk)
 - NIH Toolbox Social Relationship Scales (loneliness, stress)
 - INQ (defeat, entrapment, perceived burdensomeness, and thwarted belongingness)
 - PHQ-9 (depression)
 - GAD-7 (anxiety)
 - COVID-19 beliefs and practices survey (brief)

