9.1 Caring Contacts with Introductory Call (CC+)

Caring Contacts will consist of one introductory phone or video conversation to establish a connection between the study participant and the follow-up specialist. The introductory phone call will be unscripted, but will generally include the following elements: an introduction, if appropriate (based on participants' survey scores) a safety/wellbeing check, a review and discussion of the elements of mental distress on which the participant scored highest, a discussion of any relevant resources that may be helpful to the participant, and a description of what to expect with the caring text messages that will

follow. Hotline follow-up specialists will attempt to complete the phone call over a two-week period following study enrollment. If the phone call cannot be completed in two weeks, the Hotline will initiate the text message portion of the intervention.

The call will be followed by a series of 11 personalized caring contacts sent over the course of 6 months via text message or email.¹¹² The frequency and cadence of caring text messages will be consistent for all participants and was determined following consultation with PLES Advisors to ensure it is culturally and age appropriate. Caring text messages will be sent using a HIPAA-compliant program called Mosio according to the following schedule: weeks 1, 2, 3, 4, 6, 8, 10, 12, 16, 20, and 24. While there is no expectation that participants respond to the text messages, some participants may choose to respond. Hotline Follow-Up Specialists will review incoming text messages and phone calls from study participants and will respond according to the Hotline's internal operating procedures. These additional contacts will take place outside of the structured study protocol and will not be under the purview of SLHS institutional policies. Mosio will track the number and content of individual responses to study text messages, and this information will be shared with the study team. Response and ongoing contacts as part of the Hotline's processes will not alter the timing or frequency of caring contacts established by the study protocol. Data collected and stored in Mosio will become part of the study dataset and may be analyzed as part of process evaluation or other analyses.

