9.2 Caring Contacts without an Introductory Call (CC)

Participants will be sent caring text messages according to the schedule above. No introductory phone or video call from the Hotline will be made.

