9.3 Definition of Full Intervention

Participants must be sent at all 11 caring text messages (all participants), and complete a phone call (if randomized to CC+) to be included in the Per Protocol analysis group.

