Access to healthcare and mental healthcare services	Aim 2 Baseline Survey; Aim 2 Outcome Survey	REDCap
Domestic violence	Aim 2 Baseline Survey	REDCap
Local COVID-19 prevalence	CDC or Idaho Department of Health & Welfare Prevalence Data	
Process Variables		
Aim 1 proportion of eligible participants completing survey	REDCap	
Aim 2 proportion of eligible participants enrolled	REDCap	

MHAPPS Trial Protocol
SLHS Applied Research
December 30,2020

Participant feedback on phone call (CC+ arm only)	Aim 2 Outcome Survey	REDCap	
Participant feedback on content and timing of caring messages; satisfaction with caring contacts	Aim 2 Outcome Survey	REDCap	
Rating of quality of "connectedness" with participant		Mosio and/or REDCap	
"Dose" of follow-up contact: timing, type (phone vs text), and number of attempted and successful contacts from the Hotline		Mosio and/or REDCap	
"Dose" of Caring Contact text messages: date/time of each text message sent (* 11 text messages)		Mosio and/or REDCap	
Other Variables	Tool	Aim Collected	Source
Does cell phone on record belong exclusively to study participant or is it shared?		Aim 2 Baseline Survey	REDCap
Cell phone number, email address, contract preferences, mailing address, and alternative modes of contact		Informed Consent Form, Aim 1 Survey; Aim 2 Baseline Survey	REDCap
Eligibility and willingness to be contacted about Aim 2 participation		Aim 1 Survey	REDCap
Death		CDC or Idaho State Vital Records	

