5.3 Analysis Populations

1. Aim 1: All participants who complete the survey will be included in the data tabulations.
2. Aim 2:
 - a. **Intention to Treat (ITT) Population:** Data for all participants that complete study enrollment and the baseline survey will be included in this dataset. The primary and secondary endpoints will be evaluated in this group.
 - b. **Safety Analysis Population:** All safety analysis will include all participants who completed study enrollment and the baseline survey (equivalent to the ITT population).
 - c. **Per-Protocol Analysis Population:** The per-protocol analyses will include the subset of participants who were retained for the duration of the study and completed the assigned intervention as outlined in protocol section 9.
 - d. **Additional Populations:** Additional populations may be used to complete sensitivity analyses, for example, where missing data have been imputed using different techniques.

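### The per-protocol set requires a completed call in CC+ with no matching condition in CC, so this secondary contrast is open to selection bias in either direction

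*Protocol*

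**What the plan says.** Protocol 5.4 limits the per-protocol set to people in either arm who stay to the end and have every one of the 11 texts sent to them. It then adds a condition for one arm only: they must have "received a phone call if randomized to the CC+ intervention". Protocol 9.3 states the same condition: CC+ participants must "complete a phone call (if randomized to CC+) to be included in the Per Protocol analysis group". SAP 5.3 takes those "retained for the duration of the study and completed the assigned intervention as outlined in protocol section 9" and adds no rule of its own.

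In the CC arm, Protocol 9.2 says: "No introductory phone or video call from the Hotline will be made". For CC+ participants who are not reached, Protocol 9.1 says: "If the phone call cannot be completed in two weeks, the Hotline will initiate the text message portion of the intervention". They therefore receive texts only, as in CC, and then leave the per-protocol set.

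Protocol 13.1 commits to both an ITT and a per-protocol analysis. SAP 5.3 assigns the primary and secondary endpoints to the ITT population. SAP section 7 gives no per-protocol model, covariates or weighting, and neither document plans a complier analysis. Call data will be available: Protocol 9.4 will measure the share of CC+ reached within two weeks, and Table 2 in Protocol 12.1 lists the "number of attempted and successful contacts from the Hotline".

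**The concern.** Sending a text depends on the Hotline and the platform. Completing a call depends on the participant. The call condition therefore selects on behaviour after randomisation, and it does so in one arm only. If people who take the call would have had different 6-month loneliness anyway, the two per-protocol groups differ even when the call does nothing. Such a link is plausible, because the outcome is loneliness and the proposed mechanism is social connection, but the documents do not report one.

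What is at stake is the value of the adherence analysis. The trial asks whether adding a call helps. If many calls fail and the ITT difference is small, readers will turn to the per-protocol result, and as defined it could depart from ITT through selection alone.

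**Working it through.** **Inputs from the documents.** 165 per arm in each stratum, 70% minimum retention, a 5-unit difference, 80% power (Protocol 13.2), and two-sided alpha of 0.05 (Protocol 13.1).

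**Inputs not in the documents (assumed).** Call completion p, shown at 90%, 70% and 50%. The gap, meaning mean 6-month loneliness of non-takers minus takers, shown at 2, 3 and 5 units. The SD, shown at 13.5 and 10.

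**Step 1: the plan's own figure.** Retained per arm: 165 x 0.70 = 115.5. No SD is stated, so the 80% cannot be confirmed directly. Solving for the SD gives 5 / [(1.960 + 0.842) x sqrt(2/115.5)] = 13.6, or 13.5 with 115 per arm. At SD 13.5 and 115 per arm, power is 80.2%. At SD 10 it would be 96.6%. The design therefore implies an SD of about 13.5, and SD 10 is the less consistent choice.

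**Step 2: bias with no true effect.** Set the takers' mean to 0 and the non-takers' mean to the gap. The CC per-protocol mean is (1 - p) x gap and the CC+ per-protocol mean is 0. The bias is therefore (1 - p) x gap.

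**Step 3: false-positive rate.** SE = SD x sqrt[1/115 + 1/(115p)]. At p = 70% the CC+ group is 80.5, so SE is 1.96 at SD 13.5 and 1.45 at SD 10. With z = bias/SE, the two-sided rejection rate is Φ(z - 1.96) + Φ(-z - 1.96).

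| p | Gap | Bias | Rate, SD 13.5 | Rate, SD 10 |
|---|---|---|---|---|
| 90% | 2 | 0.2 | 5.1% | 5.3% |
| 90% | 3 | 0.3 | 5.3% | 5.6% |
| 90% | 5 | 0.5 | 5.9% | 6.6% |
| 70% | 2 | 0.6 | 6.1% | 7.0% |
| 70% | 3 | 0.9 | 7.4% | 9.5% |
| 70% | 5 | 1.5 | 11.9% | 17.8% |
| 50% | 2 | 1.0 | 7.4% | 9.5% |
| 50% | 3 | 1.5 | 10.6% | 15.3% |
| 50% | 5 | 2.5 | 20.9% | 34.0% |

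**Step 4: simulation check.** 8,000 trials per setting, 165 randomised per arm, p = 70%, SD 13.5, overall retention 70%.

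- Gap 5, retention unrelated to call-taking: bias 1.54, rejection rate 12.4%.
- Gap 5, retention 80% in takers and 47% in non-takers: bias 0.95, rate 8.3%. By formula, the share of takers among those retained is 0.7 x 0.80 / 0.70 = 0.80, so the bias is 0.20 x 5 = 1.0.
- Gap 5, retention 90% and 23%: bias 0.5, rate 6.0%.
- Gap 5, every non-taker lost: bias about 0.
- Gap -5, retention unrelated to call-taking: bias -1.49, against CC+, rate 12.2%.
- Comparing all retained participants as randomised: bias about 0, with rates of 4.7% to 5.7% across all settings run.

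**The case against.** The strongest reply is that no planned conclusion rests on this set. The primary and secondary endpoints are evaluated in ITT, and the SAP specifies no per-protocol test, so a false-positive rate describes a test the plan has not written down. This stands, and it limits the point to a supportive analysis. A reader might infer that the trial could recommend the call on a selection artefact. The documents do not support that, because nothing in them ties a recommendation to the per-protocol result.

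A reader might also infer that CC participants enter the set however hard they are to reach. That goes too far. Aim 2 consent was by phone or video in both arms (Protocol 5.2), a cell number and email were required (Protocol 5.3), and both arms must be retained. These filters shrink the bias, as Step 4 shows. They remove it only if every non-taker is also lost.

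A third inference, that the rule favours CC+, is not supported either. Lonelier people may be more willing to take a supportive call, and the bias would then run against CC+.

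Baseline adjustment could also help. SAP 7.2.1 adjusts the primary model for baseline loneliness. If carried over to the per-protocol analysis, which the SAP does not say, this would remove the part of the gap that baseline loneliness explains. Finally, a 5-unit gap equals the whole target effect, so the largest rates in the table are upper illustrations.

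**Conclusion.** The asymmetry is in the text of both documents and nothing in the plan corrects for it. The per-protocol contrast should not carry inferential weight as a test of the call. The ITT result is untouched, and the direction of the bias cannot be known in advance.

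At 70% completion and gaps of 2 to 5 units, the spurious difference is 0.6 to 1.5 units. The false-positive rate is about 6% to 12% at the SD the stated power implies, or 7% to 18% at SD 10. It is about 5% to 7% at 90% completion and about 7% to 34% at 50%. These figures rest on assumed completion, gap and SD. They also take retention as unrelated to call-taking and the full gap as remaining after any baseline adjustment. Relaxing either of those last two makes them smaller. This is a worthwhile low-cost improvement to a supportive analysis and does not threaten the trial's main conclusion.

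**What to change.** In the SAP, label the per-protocol contrast descriptive and attach no inferential claim to it. Add a complier-average causal effect as the supportive adherence analysis, estimated separately in patients and in providers/staff. Use randomised arm as the instrument for introductory call completed, by two-stage least squares, with baseline loneliness as covariate, robust standard errors and the same missing-data handling as the ITT analysis. The CC arm is not offered the call, so non-compliance is one-sided and the point estimate is essentially the ITT effect divided by p. Define call completed for this purpose, including whether a time limit applies, since Protocol 5.4 and 9.3 state none.

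The cost is SAP wording and one model, using contact data already planned for collection. There are three drawbacks to state. The interval is wider. The estimate rescales the ITT effect and adds no independent evidence. The exclusion restriction is only approximate: under Protocol 9.1 and 9.2, assignment to CC+ may change when texts start while a call is pending, and it adds call attempts even for people who never complete one.
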